### 3.8.2 QOLIE-31-P

The QOLIE-31-P is an adaptation of the original QOLIE-31 (Cramer et al, 1998). The QOLIE-31-P includes 30 items grouped into 7 multi-item subscales (seizure worry [5 items], overall quality of life [2 items], emotional well-being [5 items], energy/fatigue [4 items], cognitive functioning [6 items], medication effects [3 items], and social function [5 items]) and a health status item. The QOLIE-31-P total score, subscale scores, and health status item score are calculated according to the scoring algorithm described below, with scores ranging from 0 to 100 and higher scores indicating better functioning. In addition to these 31 items, the QOLIE-31-P includes 7 items assessing the degree of “distress” associated with the topic of each subscale (ie, distress items) and 1 item asking about the relative importance of each subscale topic (ie, prioritization item).

#### *Subscale Scores*

As a first step to calculating the subscale scores, the individual responses for the 30 subscale items are rescaled to a 0 to 100 scale with higher scores reflecting better functioning; the rescaled values for each item are defined in Section 13.1. Each subscale score is then calculated by summing the rescaled responses for that subscale and dividing by the number of items without a missing response. A subscale score will be calculated only if at least 50% of the items within the subscale are present.

#### *Total Score*

Total score is calculated as a weighted sum of the subscale scores based on the weighting in Section 13.1. Total score will be missing if at least 1 subscale score is missing. Total score will range from 0 to 100 with a higher score reflecting better functioning.

#### *Health Status Item*

Responses for the health status item is a multiple of 10 ranging from 0 to 100 with a higher score corresponding to a better health status. The health status item response is analyzed without rescaling.

#### *Distress Items*

Each subscale includes 1 distress item. The response for each distress item is an integer ranging from 1 to 5. The response for each distress item will be converted to a 0 to 100 scale (ie, 0, 25, 50, 75, and 100) with a higher score corresponding to greater distress.

#### *Prioritization Item*

The response for each subscale for the prioritization item is an integer ranging from 1 to 7. The prioritization ranking is analyzed without rescaling.

### 3.8.3 HADS

The HADS assessment consists of 14 items that are each scored on a 4-point scale ranging from 0 to 3, with a higher score corresponding to worse anxiety or depression. The depression and anxiety scores will be calculated by summing the scores for the items corresponding to each subscale, as described in the Hospital Anxiety and Depression Scale Manual (Snaith and Zigmond, 1994): the depression score is calculated as the sum of all even-numbered items; the anxiety score is calculated as the sum of all odd-numbered items.

Scores for each subscale range from 0 to 21, with higher scores corresponding to a greater level of anxiety or depression.

Missing items will be replaced by the mean of non missing items from the same subscale when calculating the above, provided at least 50% of the items (ie, at least 4 of 7 items) within the subscale are present. A subscale score will not be calculated if more than 50% of the items are missing within a subscale. This rule applies separately to the subscale scores for anxiety and depression; for example, it may be possible to calculate the depression score in cases where the anxiety score is not calculated due to non response.

### **3.8.4 Subject site transfers**

Subjects may have transferred from one site to another through the course of participation in the study. Subjects that transferred from one site to another site, for whatever reason, have generally retained their subject number. However, in some cases, the subject number changed. When this is true, the most recently assigned subject number will be used for analyses and subject data listings. A record of any change in subject numbers will be presented in the Section 13.2.

## **4 STATISTICAL/ANALYTICAL ISSUES**

### **4.1 Adjustments for Covariates**

No statistical testing is planned; therefore, this section is not applicable.

### **4.2 Handling of Dropouts or Missing Data**

Seizure frequency will be calculated over non missing diary days during each study period or time interval as described in Section 3.8.1; diary days for which seizure data were not obtained will not be considered in the calculation of seizure frequency. Because the evaluation of efficacy is not the primary objective of this study, and because this is an uncontrolled study in a variable setting which allows individualized optimization of dosing of BRV and concomitant AEDs, no summaries assessing the impact of missing seizure diary days are planned.

For subjects who prematurely discontinue during the Evaluation Period, the calculation of seizure frequency will be based on available seizure diary data while the subject was receiving BRV. The presence of dropouts may influence the evaluation of the long-term outcomes for subjects who either do not discontinue or do not discontinue early in the study. Therefore, as described below, selected summaries will be produced by exposure duration cohorts to allow an assessment of long-term outcomes without the potentially confounding influence of earlier discontinuations.

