#### 2.1.2 Secondary objectives

To evaluate the maintenance of efficacy over time of BRV.

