### 3.2.7 Exposure duration and exposure duration cohorts

At the final analysis, the overall duration of exposure (or On Treatment Period) will be calculated as the date of last dose of BRV minus the date of first dose of BRV plus 1 day.

Each subject will be classified into one or more of the following exposure duration cohorts based on the duration of BRV exposure as calculated above:

|              |           |
|--------------|-----------|
| All subjects | ≥1 day    |
| ≥3 months    | ≥90 days  |
| ≥6 months    | ≥180 days |
| ≥12 months   | ≥360 days |

This categorization will continue in 6-month increments past 12 months up to a time point that will be determined based on cumulative exposure at the time of the database lock.

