#### 8.2.2 Percent reduction in POS frequency

Percent reduction in POS frequency from Baseline to the On Treatment Period will be calculated as follows, where On Treatment Period Frequency is the 28-day adjusted POS frequency during On Treatment Period and Baseline Period Frequency is the 28-day adjusted POS frequency during the Baseline Period of the previous study.

$$\% \text{ Reduction} = 100 \times \frac{\text{Baseline Period Frequency} - \text{On Treatment Period Frequency}}{\text{Baseline Period Frequency}}$$

A similar calculation applies to each 3-month time interval over the On Treatment Period and for the cohort interval for each exposure duration cohort.

Percent reduction from Baseline for POS frequency will be summarized with quantitative descriptive statistics for the On Treatment Period, and by 3-month time intervals over the On Treatment Period. The summary over the On Treatment Period will include all subjects in the Efficacy Analysis Set. Similar summaries will be provided for the full cohort interval and by 3-month time intervals for each exposure duration cohort. Percent reduction from Baseline for POS frequency will be summarized in the same manner by geographic region.

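### The exposure-duration cohorts hold the subject mix fixed but do not remove the influence of discontinuation, so SAP 4.2 claims more for the long-term POS results than they can bear

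*SAP*

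**What the plan says.** SAP 4.2 first warns that "The presence of dropouts may influence the evaluation of the long-term outcomes for subjects who either do not discontinue or do not discontinue early", and then offers the cohorts as the remedy: "selected summaries will be produced by exposure duration cohorts to allow an assessment of long-term outcomes without the potentially confounding influence of earlier discontinuations".

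SAP 3.2.7 forms the "exposure duration cohorts based on the duration of BRV exposure as calculated above". Exposure "will be calculated as the date of last dose of BRV minus the date of first dose of BRV plus 1 day". The cut-offs are 90, 180 and 360 days, then 6-month steps, and a subject may belong to several cohorts. For percent reduction in POS frequency, SAP 8.2.2 adds: "Similar summaries will be provided for the full cohort interval and by 3-month time intervals for each exposure duration cohort". SAP 8.2.1 does the same for the frequency itself.

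For the 3-month efficacy rows, SAP 3.2.5 counts a subject only if the last BRV dose falls on or after the final day of the interval and at least one diary day exists in it.

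Lack or loss of efficacy is a reason for stopping in protocol 9.3 and a disposition category in SAP 5.1. The secondary objective is "To evaluate the maintenance of efficacy over time of BRV" (SAP 2.1.2). Protocol 13.4.2 also plans results by length of exposure, because subjects leave at different times, but does not say that this removes any distortion. That assurance appears only in the SAP.

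**The concern.** Cohort membership is settled after Baseline, by staying. A subject whose effect fades and who stops before day 360 is absent from the ≥12-month cohort from Day 1 onward, including the months when the drug still worked. Discontinuation has become the selection rule for the cohort, so its influence is still there in another form.

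What is at stake is how the secondary objective is read. A reader who takes SAP 4.2 at its word will treat a stable POS reduction in a long cohort as evidence of maintained efficacy, when it may partly show that those who lost efficacy have gone.

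**Working it through.** The plan states no figure on this point, so there is nothing to reproduce. The check has three parts.

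**1. Apply the rules.** Exposure E = last dose date − first dose date + 1. With 30-day months (SAP 3.2.5), a subject is in the k-month cohort if E ≥ 30k, and in the j-th 3-month efficacy row only if E ≥ 90j.

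| Last dose on day | Cohorts beyond all subjects | 3-month efficacy rows |
|---|---|---|
| 89 | none | none |
| 350 | ≥3, ≥6 | Months 1-3 to 7-9 |
| 360 | ≥3, ≥6, ≥12 | Months 1-3 to 10-12 |
| 700 | ≥3, ≥6, ≥12, ≥18 | Months 1-3 to 19-21 |

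Ten days separate the second and third subjects, yet only the third contributes Months 1-3 data to the ≥12-month cohort. The all-subject 3-month rows share the selection: the second subject is missing from Months 10-12, and the first is in no row.

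**2. Look for a POS result over time that accounts for leavers.**
- On Treatment summary (SAP 8.2.1, 8.2.2): keeps the whole Efficacy Analysis Set, but averages each subject over his or her own exposure, so it has no time axis.
- All-subject 3-month rows and cohort tables: have a time axis, but leave out those who stopped.
- Kaplan-Meier retention (SAP 5.1): takes permanent discontinuations for any reason as events and is not linked to seizure response.
- Overall seizure freedom (SAP 8.2.3): counts exposure shorter than the required duration as failure. It is an all-seizure outcome, not POS reduction, and its by-cohort version again uses only those who stayed.

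None does both for POS.

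**3. Illustrate direction and possible size.** From the documents: n = 108 (SAP 2.4), and reduction = 100 × (Baseline − on-treatment)/Baseline (SAP 8.2.2). Everything else is assumed: on-treatment to Baseline ratio log-normal with median 0.70 and log-SD 0.6 (true median reduction 100 × (1 − 0.70) = 30%); Baseline median 9 seizures per 28 days; 24 months of possible follow-up for all; stopping at 10% a year, except in poor responders (current rate above 75% of Baseline), where it varies; 400 runs.

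Nobody loses effect; median % reduction:

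| Poor responders stopping per year | On Treatment, all | ≥12-month cohort | ≥24-month cohort | Mean n in ≥24 |
|---|---|---|---|---|
| 10% | 29.5 | 29.7 | 29.7 | 88.0 |
| 30% | 30.0 | 34.4 | 38.4 | 72.7 |
| 50% | 30.9 | 39.5 | 44.9 | 61.1 |
| 70% | 31.5 | 44.0 | 49.2 | 53.1 |

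20% a year lose effect (rate returns to Baseline, or stays above it):

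| Poor responders stopping per year | ≥24 cohort, Months 1-3 | ≥24 cohort, Months 22-24 | Decline (points) | Months 22-24 had all been observed |
|---|---|---|---|---|
| 10% | 28.0 | 11.0 | 28.0 − 11.0 = 17.0 | 11.0 |
| 30% | 35.6 | 19.9 | 35.6 − 19.9 = 15.7 | 11.1 |
| 50% | 43.3 | 32.5 | 43.3 − 32.5 = 10.8 | 10.9 |
| 70% | 48.7 | 42.3 | 48.7 − 42.3 = 6.4 | 11.1 |

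When stopping is unrelated to response (10% rows), the cohort agrees with the truth. When poor responders stop more often, its level is too high. The decline is hidden to any extent only when the link is strong: at 30% it is 15.7 points against 17.0.

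**The case against.** The best defence is the SAP's own preceding sentence, which directs the concern at subjects who stay. For them a fixed cohort does what is needed, since successive intervals compare the same people. That stands, and it is a reason to keep the cohorts. It does not carry the final clause, which offers an assessment of long-term outcomes with no such limit.

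It also stands that the study is descriptive with safety as its primary objective, so no error rate is affected. POS reduction is listed among the other efficacy variables; the named secondary variable is BRV monotherapy (SAP 2.2.2). Disposition by reason, retention and overall seizure freedom are all reported. And nothing shows that dropout here depends on response. The parent studies were stopped because a positive efficacy outcome had become too unlikely (protocol 6.4), and some entrants had met exit criteria (SAP 3.2.3). That makes such dropout plausible, not established.

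Three stronger readings go too far:

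- A reader might infer that leavers vanish from the POS results altogether. They remain in the On Treatment summary and in every cohort shorter than their own exposure.
- A reader might infer that longer cohorts must look better and flatter. That needs response-related dropout, and for flatness a strong link. Some short exposure may also reflect sponsor closure.
- A reader might infer that leavers should be counted as non-responders. That mixes retention with efficacy. Suppose 38% have a reduction of at least 50%, nobody loses effect, and 10% of everyone stops per 3-month interval. After three intervals the share reads 38% × 0.9³ = 38% × 0.729 ≈ 28%, an apparent decline with no loss of effect. SAP 5.1 also places withdrawals recorded as unrelated to AEs or lack of efficacy under subject choice.

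**Conclusion.** The clause in SAP 4.2 is wrong as written, in a limited way. The cohorts remove changes in subject mix between intervals; they do not remove selection by later retention. The bias is towards too favourable a result if poor responders leave more often, and absent if dropout is unrelated to response.

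Its size cannot be computed from the documents, which give no dropout rates by reason. In the illustration with 20% a year losing effect, the overstatement at Months 22-24 runs from 0 points (11.0 − 11.0) through 8.8 (19.9 − 11.1) and 21.6 (32.5 − 10.9) to 31.2 (42.3 − 11.1) as stopping among poor responders rises from 10% to 70% a year. Those values rest wholly on the assumed response distribution and rates. The consequence is for what can be concluded about maintenance of efficacy, and it justifies a correction and one supplementary table.

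**What to change.** 1. **SAP 4.2.** Replace the closing clause with a statement of three things: the cohorts keep the same subjects across intervals; cohort and by-interval POS results apply only to subjects who remained on BRV that long; and these results may overstate maintenance of efficacy if poor responders stop sooner.

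2. **SAP 8.2.2.** Add one supplementary table beside the cohort tables, with the full Efficacy Analysis Set as denominator. For each 3-month interval give the number and percentage:
   - on BRV with a POS reduction of at least 50%;
   - on BRV with a smaller reduction;
   - off BRV, by reason: lack or loss of efficacy, AE, subject choice, lost to follow-up, other or missing, and sponsor closure or transfer to continued BRV.

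   Do not impute leavers as non-responders. A line for subjects on BRV without diary data in the interval would let the rows add up.

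3. **Transfers.** Identify these separately from the termination data. Subjects moving to another BRV study or an access program complete an Early Discontinuation Visit (protocol Table 5:1 footnotes), which classes a subject as discontinued under SAP 3.2.4, and SAP 5.1 has no transfer category.

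The cost is a change of wording, one extra table, the work of separating transfers, and a 50% threshold that the SAP does not now contain. The long-term picture may look less favourable.

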### **4.3 Interim Analyses and Data Monitoring**

Interim summaries may be produced to support regulatory submissions for marketing authorization while this study is ongoing. There are no statistical concerns with such interim assessments for this study design.

### **4.4 Multicenter Studies**

Efficacy and safety outcomes will not be assessed for individual investigator sites due to the low expected number for enrollment within each investigator site.

#### 4.5 Multiple Comparisons/Multiplicity

No statistical testing is planned; therefore, this section is not applicable.

#### 4.6 Use of an “Efficacy Subset” of Subjects

All subjects who receive at least 1 dose of study drug and have at least 1 diary record during the Evaluation Period will be included in efficacy summaries. No additional efficacy subsets are defined for the study.

#### 4.7 Active-Control Studies Intended to Show Equivalence

This section is not applicable for this study.

[figure not shown]
#### 4.8 Examination of Subgroups

Selected summaries will be provided for the following subgroups as specified within each of the following sections:

- Two mappings of countries to regions are defined, 1 based on the classification requested by Food and Drug Administration (FDA), and 1 based on the regional classification for the CHMP (Committee for Medicinal Products for Human Use).

[figure not shown]
Countries will be mapped to geographic regions as follows for the FDA:

| Geographic Region (FDA) | Country |
|-------------------------|---------|
|-------------------------|---------|

Countries will be mapped to geographic regions as follows for the CHMP:

| Geographic Region (CHMP) | Country |
|--------------------------|---------|
|--------------------------|---------|

\* [REDACTED]

- Subject’s exit status in the prior trial (eg., =1 if met exit criteria in prior trial, =0 otherwise)

## 5 STUDY POPULATION CHARACTERISTICS

### 5.1 Subject Disposition

Due to differences in data format across studies, in order to facilitate summary of subject disposition, the reasons for discontinuation for individual studies will be collapsed as follows for summaries:

| LTFU Category     | CRF Reason  |
|-------------------|---|
| ADVERSE EVENT     | ADVERSE EVENT   |
| LACK OF EFFICACY  | LACK OF EFFICACY  |
|                   | LOSS OF EFFICACY  |
| LOST TO FOLLOW-UP | LOST TO FOLLOW-UP   |
| SUBJECT CHOICE    | CONSENT WITHDRAWN   |
|                   | WITHDRAWAL OF CONSENT FOR PERSONAL REASONS NOT RELATED TO AES                     |
|                   | WITHDRAWAL OF CONSENT FOR PERSONAL REASONS NOT RELATED TO AES OR LACK OF EFFICACY |
| OTHER             | PROTOCOL VIOLATION  |
|                   | OTHER REASON  |
|                   | OTHER   |
| MISSING           | If subject discontinued the study and the termination CRF is not available        |

Only 1 primary reason for discontinuation should have been reported. In the event that more than 1 reason is specified in the clinical database, both reasons will be summarized and a footnote will be added to the summary table to indicate that at least 1 subject is counted for multiple reasons for discontinuation.

An overall summary of disposition will be provided for all enrolled subjects (ie, all subjects who signed informed consent). The following will be summarized:

- The number of subjects in the Safety Analysis Set
- The number of subjects excluded from the Safety Analysis Set
- The number of subjects completed the study
- The number of subjects who have discontinued from the study, including the reason for discontinuation. If subject discontinued the study and the termination CRF is not available, the reason for discontinuation will be reported as “MISSING”.

Additionally, an overall summary of disposition will present the following for subjects in the Safety Analysis Set:

- The number of subjects completing the study The overall number of subjects discontinuing and the number of subjects discontinuing by primary reason for discontinuation. If subject discontinued the study and the termination CRF is not available, the reason for discontinuation will be reported as “MISSING”.

Overall subject disposition will also be summarized by geographic region for the Safety Analysis Set.

The number of subjects within each geographic region will be summarized for the Safety Analysis Set.

Kaplan-Meier estimates of the percentage of subjects completing 3, 6, 12, 24, 36, 48, and 60 months of treatment with BRV will be provided. This analysis will be based on the duration of exposure to BRV as defined in Section 3.2.7. Subjects who have permanently discontinued will be analyzed as events on the last day of treatment with study drug; subjects who complete the study will be censored on the last day of treatment with study drug.

The date of first subject in (date of earliest Visit 1), date of last subject out (date of last scheduled or unscheduled visit), number of enrolled subjects, and the number of subjects in each analysis set or indication will be summarized overall and by investigator site. Subjects who transferred sites will be summarized according to their original site.

## 5.2 Protocol Deviations

The number and percentage of subjects with at least 1 important protocol deviation will be summarized overall and by category of protocol deviation for the Safety Analysis Set.

## 6 DEMOGRAPHICS AND OTHER BASELINE CHARACTERISTICS

### 6.1 Demographics

Demographics summaries will be based on demographic data from follow-up studies for subjects who enrolled in a follow-up study that collected demographic data. Otherwise, demographics summaries will be based on demographic data collected in the previous double-blind study.

Age, age category (<17, 17 to <65, and  $\geq 65$  years), gender, racial group and overall racial group (see below), body weight (kg), height (cm), body mass index (BMI) ( $\text{kg}/\text{m}^2$ ), and BMI category ( $<18.5$ ,  $18.5$  to  $<25$ ,  $25$  to  $<30$ ,  $30$  to  $<40$ ,  $\geq 40$ ) will be summarized for the Safety Analysis Set. Demographic data will be summarized overall and by subgroup for geographic region.

Racial group was not collected in a consistent manner across studies. For this reason, racial group will be collapsed as follows for statistical summaries:

| Category                           | CRF Racial Group                         |
|---|---|
| American Indian/Alaskan Native            | American Indian/Alaskan Native                  |
| Asian                                     | Asian, Asian/Pacific Islander, Indian/Pakistani |
| Black                                     | Black, African-American                         |
| Native Hawaiian or Other Pacific Islander | Native Hawaiian or Other Pacific Islander       |
| White                                     | White, Caucasian, Hispanic                      |
| Other/Mixed                               | Other, Other/Mixed, Mixed Race                  |

moreover, the overall racial group will be collapsed as follows for statistical summaries:

| Category | Racial Group from Previous Study  |
|-----------------|--|
| White           | White, Caucasian, Hispanic   |
| Black           | Black, African-American  |
| Asian           | Asian, Native Hawaiian or Other Pacific Islander, Asian/Pacific Islander, Indian/Pakistani |
| Other           | American Indian/Alaskan Native, Other, Other/Mixed   |

All subjects should be classified into one of the above categories.

Racial group, ethnicity (Hispanic or Latino, Not Hispanic or Latino), and racial subgroup (Indian/Pakistani, Japanese, Other) will be provided in subject data listings.

